13.7.2. Other Safety Endpoints

Clinical laboratory assessments (chemistry, hematology, renal function, coagulation, and urinalysis), vital signs, ECG findings, physical examination findings, and weight and height will be summarized descriptively.

13.7.3. Prior and Concomitant Medications

Prior and concomitant medications will be coded by PT using the most recent World Health Organization Drug Dictionary (WHODrug) version (December 2017 or later). The number and percentage of patients in the Safety Analysis Set with concomitant medications will be tabulated by Anatomical Therapeutic Chemical classification pharmacological subgroup and WHODrug PT by dose level.

At each level of summarization, a patient will be counted once if 1 or more medications at that level have been reported for that patient.

13.8. Exploratory Analysis

Change from Baseline to Week 144, Week 192, and Week 284 in **CCI** score is the exploratory variable for this study.

Exploratory analyses of scores from the **CCI** assessments will be performed using descriptive statistics for actual values and changes from Baseline, by visit, for each age cohort and overall. Graphical representations will be produced, as appropriate.

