Efficacy The efficacy of eteplirsen will be assessed by evaluating the change in NSAA scores from Baseline to the end of Week 144, Week 192, and Week 284.	
STATISTICAL METHODS:	
Sample Size As this study is an OLE study of Study 4658-102, the sample size will be predicated on the sample size of Study 4658-102.	
Safety Analyses Adverse events will be coded using the Medical Dictionary for Regulatory Activities (MedDRA) Version 20.1 or higher. An AE will be defined as a treatment-emergent adverse event (TEAE) if it developed or worsened in the period from the first dose of study drug to 28 days after the last dose of study drug. A treatment-related TEAE will be defined as a TEAE that the Investigator considered related to the study treatment.	

NAME OF COMPANY Sarepta Therapeutics, Inc. [name] [contact]	NAME OF FINISHED PRODUCT Eteplirsen Injection
	NAME OF ACTIVE INGREDIENT Eteplirsen

Congenital anomaly/birth defect: A congenital anomaly/birth defect that occurs in the offspring of a patient exposed to the investigational product.Important medical event: An AE that may not result in death, be life-threatening, or require hospitalization may be considered an SAE when, based upon appropriate medical judgment, the event may jeopardize the patient and may require medical or surgical intervention to prevent one of the outcomes listed above.	

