2. SCHEDE OF EVENTS

The schedule of study events is presented in [Table 2](#).

Evaluations should be performed in the order in which they appear below.

On infusion days, all evaluations should be performed prior to infusion, except vital signs, which should be assessed before and after the infusion.

Table 2: Schedule of Events

Visit/Week	BL	Weekly Visits																								284 (End of Study ^k)	288 (Safety Follow-up ^l)	
		1 ^a	12 ^a	24	36	48	60	72	84	96	108	120	132	144	156	168	180	192	204	216	228	240	252	264	276			
Informed Consent	X																											
Inclusion/Exclusion Eligibility	X																											
Safety Laboratory Assessments ^b	X ^c		X	X	X	X	X	X	X	X	X	X	X	X	X	X	X	X	X	X	X	X	X	X	X	X	X	
Vital Signs ^d																												X
Weight																												
Urine dipstick testing																												
Renal function blood tests ^m	X	X	X	X	X	X	X	X	X	X	X	X	X	X	X	X	X	X	X	X	X	X	X	X	X	X		
Quantitative urine analysis ⁿ	X	X	X	X	X	X	X	X	X	X	X	X	X	X	X	X	X	X	X	X	X	X	X	X	X	X		
Physical Exam (including height & ulnar length) ^e	X ^c		X	X	X	X	X	X	X	X	X	X	X	X	X	X	X	X	X	X	X	X	X	X	X	X		
CCI ^{i,o}	X ^{c,j}									X																		X
ECG ^o	X ^c		X	X	X	X	X	X	X	X	X	X	X	X	X	X	X	X	X	X	X	X	X	X	X	X		
Eteplirsen Infusion ^f																												
Con Meds/Therapies Assessment																												
AE Assessment ^{g,h,i}																												

AE = adverse event; AESI = adverse event of special interest; BL = Baseline; con med = concomitant medication; ECG = electrocardiogram; EOS = end-of-study; ICF = informed consent form; CCIⁱ = CCI^j; OLE = open-label extension.

^a For Weeks 1 to 283, visits will include vital signs, weight, eteplirsen infusion, and assessments of con meds/therapies and AEs. Additionally, the Week 12 visit and visits every 12 weeks subsequently will also include safety labs, ECG, and physical exam (including height and ulnar length).

^b Safety laboratory assessments will include hematology tests (including platelets), coagulation studies, serum chemistries (including liver function).

^c These assessments will not be performed at Baseline if performed at Week 96 of Study 4658-102.

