- d. Vital signs will include blood pressure, heart rate, respiration, and axillary temperature. On infusion days, vital signs will be measured within 60 minutes prior to infusion and 30 minutes (\pm 10 minutes) after the end of the infusion. All assessments will be performed after patients have remained calm for 5 minutes. Pulse rate and respiratory rate should be measured over 1 minute.
- e. Height and ulnar length will be measured as part of every physical examination. The examination will also include general appearance; head, ears, eyes, nose, throat; heart; lungs; chest; abdomen; skin; lymph nodes; musculoskeletal system; and neurological systems.
- f. Patients will receive ~~cc~~ mg/kg of eteplirsen once a week over 35-60 minutes, and will be observed for at least 1 hour after each infusion. It is recommended that a topical anesthetic cream (eg, lidocaine 2.5%, prilocaine 2.5%, or LMX4 cream) be applied to the injection site prior to each infusion.

Once a patient begins receiving weekly eteplirsen infusions at satellite sites, all subsequent infusions should be administered at the patient's satellite site unless otherwise indicated and approved by the Medical Monitor. Patients may receive home infusions starting at Week 1. Note that an implanted venous access port may be inserted for eteplirsen administration at the discretion of the Investigator.

- g. AEs should be recorded at all visits. Spontaneously reported AEs occurring within 28 days after the last dose of eteplirsen will also be recorded.
- h. In the event that a patient experiences an AESI of infusion-related reaction, an infusion-related reaction case report form should be completed.
- i. Special situations (eg, overdose, medication error, accidental/occupational exposure) should be monitored and recorded.
- j. For patients aged \leq 3 years the revised ~~CCI~~ will be used. For patients aged >3 age-appropriate items from the ~~CCI~~ (Mercuri 2016) should be performed.
- k. Patients who are withdrawn from the study early will be asked to complete all end-of-study (EOS) assessments prior to withdrawal and within 28 days of their last eteplirsen infusion, if possible, unless they have completed a physical exam and safety labs within 28 days of withdrawal.
- l. All patients will be asked to complete the Safety Follow-up visit 28 days after their last dose of eteplirsen. Patients may transition to commercially available product if commercially available eteplirsen is available.

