10. STUDY ASSESSMENTS

10.1. Study Schedule of Events

A detailed schedule of the study assessments and time points is shown in [Table 2](#).

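### The efficacy variable needs three post-Baseline functional scores, but the functional-scale row of Table 2 shows only two post-Baseline marks

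*Combined protocol and SAP*

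**What the plan says.** The Synopsis (Efficacy) states that efficacy will be assessed by "evaluating the change in NSAA scores from Baseline to the end of Week 144, Week 192, and Week 284". Section 13.8 repeats the weeks as the exploratory variable: "Change from Baseline to Week 144, Week 192, and Week 284 in" a score whose name is redacted there.

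For timing, Section 10.1 points to one place: "A detailed schedule of the study assessments and time points is shown in" Table 2. In that table the functional-scale row has a redacted label. It can be identified from footnote j, attached to its Baseline mark, which covers the age-dependent version of the scale ("For patients aged >3 age-appropriate items from the" full scale for the older boys). The row shows three marks: one at Baseline, one in the middle of the table and one at the end. Footnote c lets the Baseline assessment be carried over from the parent study: "These assessments will not be performed at Baseline if performed at Week 96 of Study 4658-102".

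Footnote a describes the 12-weekly visits: "the Week 12 visit and visits every 12 weeks subsequently will also include safety labs, ECG, and physical exam (including height and ulnar length"). The functional scale is not in that list. Section 10.5.1 describes the scale and its scoring but gives no weeks. Section 10.2.2 lists the Baseline assessments without the scale, although Table 2 marks it at Baseline.

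**The concern.** The analysis text names three post-Baseline visits, and the schedule that sites work from appears to provide two. Sites perform what the schedule marks. If an endpoint week is unmarked, its score will not be collected routinely, and a functional score missed in a growing boy cannot be obtained later.

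The study enrols at most 15 patients and the analysis is descriptive, by visit and age cohort. There is no model that would borrow from neighbouring visits, so an unscheduled week means no planned summary for that week. This is the only efficacy variable in the readable text. Section 8.6 also times the Early Termination visit by reference to the last functional assessment visit, so an unclear functional schedule affects that procedure as well.

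**Working it through.** The plan gives no figure to reproduce. The check is a count of what the analysis needs against what the schedule marks.

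**Step 1. Required.** From the Synopsis and Section 13.8: Baseline + Week 144 + Week 192 + Week 284 = 4 assessments, of which 3 are post-Baseline.

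**Step 2. Marked.** From the functional-scale row of Table 2: 3 marks, of which 1 is Baseline and 2 are post-Baseline. The carry-over rule in footnote c supplies the Baseline value and adds no later visit.

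**Step 3. Shortfall if the row is complete.** 3 − 2 = at least 1 endpoint visit without a mark. This minimum holds wherever the two marks sit. It would be larger if either fell on a week other than 144, 192 or 284.

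**Step 4. Can one assessment serve two endpoint weeks?** Footnote o allows a 2-week window. The gaps are 192 − 144 = 48 weeks and 284 − 192 = 92 weeks, so it cannot.

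**Step 5. Does other readable text schedule the missing visit?**

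| Place | What it gives on the functional scale |
|---|---|
| Table 2, footnote a | Not among the 12-weekly additions |
| Section 10.5.1 | Scale and scoring, no weeks |
| Section 10.2.2 | Not among the Baseline assessments |
| Synopsis, Section 13.8 | Endpoint weeks for analysis, no instruction to assess |

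**Step 6. How reliable is the row as read?** The visits are Baseline, Week 1, Weeks 12 to 276 by 12 (23 visits), Week 284 and Week 288: 1 + 1 + 23 + 1 + 1 = 27. With the label, a row should have 28 cells.

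| Row | Cells | Marks as read | Expected from the text |
|---|---|---|---|
| Physical exam | 29 | 25 | Baseline + 23 + Week 284 = 25 |
| ECG | 29 | 25 | 25 |
| Renal blood tests | 29 | 26 | 12-weekly marks complete; Baseline, Week 1 and Week 284 also marked |
| Weight, infusion, concomitant medication, AEs | – | 0 | Every weekly visit (footnote a) |
| Vital signs | 29 | 1 | Every weekly visit (footnote a) |
| Functional scale | 29 | 3 | 4 |

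Rows made of separate marks kept every 12-weekly mark through Week 284. The depleted rows are mostly weekly items, which fits a single merged bar across the weekly columns. The functional row is made of separate marks, so its count of three is plausibly faithful. Its cell positions are not usable: there are 29 cells for 28 columns, and the last mark sits past the Week 288 cell.

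**The case against.** The strongest objection is that a count withstands shifted columns but not lost marks, and this table did lose content. Footnote a requires weight, infusion, concomitant medication and AE checks every week, yet those rows are blank. The urine dipstick row is blank too, although the rhabdomyolysis monitoring text following Section 10.3.4.4 relies on the schedule for it, and footnote a does not mention the dipstick, so the merged-bar explanation is not confirmed for every blank row. The functional row's own label is redacted, and one of its footnote letters (i) leads to a note about overdose and medication error. This stands as a limit on confidence. If one mark was lost, the shortfall could be zero.

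Second, the absence of other scheduling text cannot be fully verified. Sections 6.2 and 7.3.2, parts of Sections 7.1 and 7.4 and a block of the Synopsis statistics are redacted, and Section 10.5.1 refers to a Clinical Evaluator Manual that is not available. Footnote a is also not exhaustive: it omits the renal blood tests and quantitative urine analysis, which do carry 12-weekly marks. Its silence on the scale is therefore weak evidence on its own. Even so, Section 10.1 makes Table 2 the place where timing is set, so a week stated only in hidden text would still have to be reconciled with it.

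Third, the variable is exploratory and untested, in a study whose primary objective is safety. That is true, and it limits the weight of the point. It does not remove the mismatch.

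**Conclusion.** On the text as it reads, the endpoint needs three post-Baseline functional assessments and the schedule marks two. At least one of the three endpoint visits is then unscheduled. This rests on two assumptions: that the redacted row is the functional scale, which footnote j supports, and that no mark in it was lost, which the intact separate-mark rows make likely but do not prove. Confidence is moderate.

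A reader might infer three stronger things, which the documents do not support.

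- *That Weeks 144 and 192 are the missing weeks, because the middle mark appears under Week 96.* The same reading puts the final mark beyond the last visit, so position cannot name the week. A count of lost scores built on it has no firm basis either.
- *That any other marked visit would be wasted because the analysis ignores it.* Section 13.8 summarises observed scores and changes visit by visit, so such a visit would be reported.
- *That boys who leave early would give little or no endpoint data.* Section 8.6 and footnote k ask withdrawn patients for the Week 284 / end-of-study assessments, with an exception in footnote k for those recently examined.

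**What to change.** Check the functional-scale row in the original Table 2 against the Synopsis and Section 13.8, and make them agree, so that the scale is marked at Baseline and at Weeks 144, 192 and 284. Any other visit now marked may stay, since the by-visit summaries already cover it. Add the scale to the Baseline assessments in Section 10.2.2. Stating the weeks in Section 10.5.1 as well would avoid relying on a single table row.

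The cost is a table and text correction, plus one or two extra administrations of a scale already in use. Weeks 144 and 192 are existing 12-weekly visits (12 × 12 and 16 × 12), and Week 284 is the end-of-study visit. If the original row already carries all four marks, the only changes left are the small text additions.

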13.9. Other Statistical Issues

Additional analyses may be conducted. Any such analyses will be detailed in the SAP.

14. SPECIAL REQUIREMENTS AND PROCEDURES

14.1. Compliance with Ethical and Regulatory Guidelines

This study will comply with International Council for Harmonisation- Good Clinical Practice, with the latest version of the Helsinki declaration and with applicable national regulations, as well as with the European Union Directive 2001/20/EC.

14.2. Institutional and Ethics Review

Before enrollment of patients into the study, the protocol and informed consent (for parents/legal guardians) documents will be reviewed and approved by the appropriate IRB/IEC and regulatory authority. Amendments to the protocol and all substantial changes to the trial documentation will be subjected to the same IRB/IEC and regulatory authority review requirements as the original protocol. The Investigator will promptly notify the IRB/IEC and Sponsor of any SAEs or of any other information that might affect the safe use of the IP during the study. IRB approvals/IEC positive opinions and regulatory authorities' approvals must be sent to the Sponsor, or its designee, before initiation of the study or before an amendment is instituted. All correspondence with the IRB/IEC and the regulatory authority should be retained in the study regulatory files.

14.3. Informed Consent and Authorization for Use and Disclosure of Protected Health Information

Written informed consent from each patient and/or patient's parent(s) or legal guardian(s) must be obtained prior to any study-specific evaluation being performed. A copy of the signed informed consent documents will be given to the patient and/or patient's parent(s) or legal guardian(s); the Investigator will retain the original copies of these documents.

The informed consent documents, as prepared by the Sponsor or designee, must be reviewed and approved by the IRB/IEC and regulatory authorities, as applicable, before initiation of the study. The informed consent document must contain the basic required elements of consent and additional elements, as applicable per regional requirements.

14.4. Compliance with the Protocol

All processes and procedures defined in this protocol will be adhered to. Emergency departures from the protocol that eliminate an apparent immediate hazard to a particular patient and that are deemed by the Investigator as crucial for the safety and wellbeing of that patient may be instituted for that patient only and documented as deviations. The Investigator will contact the Medical Monitor as soon as possible regarding such a deviation. These departures do not require preapproval by the IRB/IEC; however, the IRB/IEC and Medical Monitor must be notified in writing as soon as possible, in accordance with the IRB/IEC policies, after the departure has been made.

14.5. Confidentiality

14.5.1. Data

All information regarding the nature of the proposed investigation that is provided to the Investigator by the Sponsor, the Sponsor's designee, or the study monitor, except for information that is required by law or regulations to be disclosed to the IRB/IEC, the patient's parent(s) or

legal guardian(s), or the appropriate regulatory authority, must be kept in confidence by the Investigator in accordance with current global data protection standards (eg, Health Insurance Portability and Accountability Act [HIPAA], General Data Protection Regulations [GDPR]).

14.5.2. Patient Confidentiality

The anonymity of participating patients will be maintained to the extent required by applicable laws and in accordance with current global data protection standards (eg, HIPAA, GDPR). Patients may be referenced by their initials and an assigned patient identification number on the eCRFs and other data collected by the Sponsor. The Investigator must maintain all documents related to the study that identify the patient (eg, the signed informed consent document) in strict confidence, except to the extent necessary to allow auditing by the appropriate regulatory authorities, the IRB/IEC, the study monitor, or the Sponsor or its representatives.

15. STUDY DOCUMENTATION AND GENERAL INFORMATION

15.1. Essential Study Documents

Essential study documents are among the critical documents required before study enrollment is to occur. Essential documents, as well as supplemental information, such as the Investigator's Brochure, Pharmacy Manual, and eCRF Completion Guidelines, as specified in the Study Manual and/or regulatory binder, must be kept onsite in a designated study site file.

The study site files will also contain, but are not limited to, patient accountability records, drug accountability (receipt/dispensing) records, Sponsor/Investigator correspondence, IRB/IEC correspondence, deviations, biological sample records, and SAE and Investigational New Drug safety reports/Safety Alert Letters.

15.2. General Information

The Investigator should refer to the current Investigator's Brochure along with subsequent Safety Alert Letters, the Study Operations Manual, Pharmacy Manual, Laboratory Manual, eCRF Completion Guidelines, and all other study-specific information that is provided during the study initiation visit or by the study monitor.

15.3. Dissemination of Study Results

The information that is developed during the conduct of this clinical study is strictly confidential. This information may be disclosed only as deemed necessary by the Sponsor. At the conclusion of this clinical study, a clinical study report will be prepared. In addition, a manuscript may be prepared for publication in a reputable scientific journal under the direction of the Sponsor. The Sponsor will publish and communicate the clinical study results, irrespective of positive or negative findings. Data generated for this study will be exclusively owned by the Sponsor, as detailed in the Clinical Trial Agreement. The study will be registered in the European Clinical Trials database and on ClinicalTrials.gov. After completion of the study, results will be disseminated through the clinical trial registries of the applicable countries.

15.4. Product Handling and Complaints Reporting

If there are any issues during the study related to the quality of the IP, the Investigator, clinical site pharmacist, or pharmacy designee should contact the Sponsor or designated CRO.

17. APPENDICES

17.1. Appendix 1: Estimated Blood Volumes to be Drawn

The World Health Organization (WHO) recommended blood volume limits should be used as a guide for blood sampling in this study ([Howie 2011](#)). Per individual, the study-related blood loss should not exceed 3% of the total volume during a 4-week period or 1% of total blood volume within a 24-hour period. [Table 3](#) summarizes the mean blood volume per body weight for patients ≤ 10 kg and [Table 4](#) summarizes the amount of blood required for individual sample collection.

Due to the limitations on the volume of blood collection that is considered to be acceptable in young children with very small total-circulating blood volumes, adjustments to sample collection will be made for patients weighing <10 kg. These adjustments include the use of 0.5-mL collection tubes for utilization of local laboratories for the coagulation panel.

Table 3: Mean Blood Volume per Body Weight

Body Weight (kg)	Mean Total Body Blood Volume (mL)	Maximum Blood Collection Volume (mL)	
		24-Hour Period (1%)	30-Day Period (3%)
5.0	400	4.0	12.0
6.0	480	4.8	14.4
7.0	560	5.6	16.8
8.0	640	6.4	19.2
9.0	720	7.2	21.6
10.0	800	8.0	24.0

Table 4: Blood Volume Requirements per Test

Test	Volume (mL)
Chemistry panel	2.0
Hematology panel	1.0
Coagulation panel ^a	2.7

^aCan be done at local laboratory in the event of blood volume limitations.
